Statistical Analysis Plan

Title: Reducing Maternal Depression and Promoting Infant Social-Emotional Health & Development

NCT03464630

Date: 09/18/2016

Analytic Strategy

Constructs. We will use a systematic approach to construct development to create two parent outcomes (mother positive/negative) and one infant outcome (infant social emotional functioning). *For our outcomes of maternal depression, parenting knowledge and stress, we will examine single indicants. To view potential intervention moderating effects, we will attempt to create a maternal contextual risk indicant (e.g., isolation/support, relationship status, conflict, economic hardship); for maternal depression prior to intervention as a potential moderator, we will view depression onset, chronicity, and severity as well as presence of other treatment including medication to examine each of these and their effect on intervention outcomes.* For factor analysis, given appropriate internal consistency and inter-rate reliability, we will examine questionnaire scales and observational codes using factor analytic techniques [99], retaining a 5:1 subject to parameter ratio. Scale factor loadings above .30 and communality estimates above .15 will be confirmed within SEM methodology to produce fit indices to view how each indicant set fits into their specified domain. If satisfactory, unit-weighting of the standardized score for each indicant will be summed. If not, we will select an index variable within each domain to represent the outcome.

Random Sampling/Attrition Analysis. Though mother-infant pairs will be randomly assigned to the intervention, condition differences may exist due to random sampling failures or differential attrition. To address this issue, 2×2 (Group x Attrition Status) MANOVAS will be performed using the baseline assessment for mother, infant and contextual risk variables. The presence of a statistically significant Group main effect would provide evidence that random assignment was not effective in equating groups. A second possible source of nonequivalence is differential attrition by condition. A Group x Attrition Status significant interaction provides evidence of differential attrition between groups. In general, analyses will proceed using an “intent to treat” approach and all participants recruited will be included in subsequent analyses.

Examination of Acute Intervention Effects (Aim 2)

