(Aims 2.1 - 2.3) Our post-assessment n, to examine acute intervention effects, is expected to be 150 (75/condition). We will initially view intervention effects on our mother/infant outcomes using a 2 (pre-post) $\times 2$ (MBN intervention group) repeated measure analysis of variance. We will examine the inter-correlations among outcomes and, if significant, will use a MANOVA approach to examining MBN intervention effects. The F test is robust to non-normality if such non-normality is caused by skewness rather than outliers. We will take appropriate measures to reduce outlier influences. **(Aim 2.4)** To examine the relations between mother change (parenting and maternal depression) and infant change, one approach will be to create individual beta estimates for mothers and infant utilizing the polynomial contrast function within MANOVA to produce individual trajectory scores reflecting parent and infant change from pre to post that can then be used in external between-condition covariate analysis. The trajectory scores will be subjected to an analysis of covariance with infant change trajectories as the dependent variable and parent change as the covariate. We will determine whether the parent change covariate is significantly related to the dependent variable (demonstrating that changes in parenting behavior and child functioning covary). We will determine the statistical significance and effect sizes of intervention effects (ignoring the covariate). We will then determine if entering the parent functioning covariate modifies the intervention effect size and statistical significance. If parent change is strongly linked to infant change, then entering the covariate should result in nonsignificant intervention effects. Estimates of covariance-adjusted effect sizes will provide estimates of the proportion of intervention effect size that can be explained by the parenting change variable. We will test for between-group heterogeneity of covariance to determine whether the strength of association between change in parenting and infant functioning differs by intervention group.

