Examination of Moderating Influences (Aim 3) Dosage & Skills Acquisition. To evaluate moderating influences on parent and infant behavior our first focus is on how maternal depression prior to intervention (*i.e.*, *chronicity, severity, receipt of psychiatric treatment/medication*) affects MBN intervention dosage (**3.1**); secondly, we are interested in the moderating effect of dosage on mother and infant change (**3.2**). For **3.1**, we will examine a 2 (hi/lo dosage) x 2 (intervention) ANOVA, using maternal depression indicants (*e.g.*, *chronicity*) as the dependent measure. A significant main effect for dosage would indicate that higher levels of maternal depression are found at different dosage levels; it is anticipated that higher depression will be evidenced in the low dosage group. A significant interaction would indicate a higher level of maternal depression is found within a dosage by condition cell. Though we would not anticipate a significant interaction, we will examine if higher levels of depression are associated with low dosage only within the Mom and Baby Net (MBN) intervention group; this could indicate that the skills focus of MBN learning may have been too intense for highly depressed mothers. For **3.2**, examining dosage as a moderating influence on mother and infant change, we will utilize the individual beta-slope estimates reflecting parent and infant change from Aim 2 as the dependent measures in separate 2 (intervention) x 2 (hi/lo dosage) ANOVA designs. We hypothesize a significant interaction term indicating the highest positive change trajectories will be for the intervention mothers with high dosage, when compared to low dosage intervention mothers and Depression and Developmental Awareness (DDAS) mothers regardless of dosage level. If a significant dose-effect relationship exists within the MBN condition, we will determine if an effective dosage level can be identified that is less than the maximum number of intervention sessions offered. **3.3** analysis will examine Pearson correlations between contextual risk and level of maternal depression and a bi-serial correlation for the relation between contextual risk and dosage (hi/lo) to determine if contextual risks are related to both initial levels of depression and subsequent engagement in intervention. To further examine the contextual risk on mother and infant change, we will form a hi/lo risk categorical variable, based on median split, and utilize the same 2 (intervention) x 2 (hi/lo risk). If a main Intervention effect is significant, we would expect MBN mothers and infants, regardless of risk level, to evidence the greatest improvements when compared to DDAS mothers. If significant interaction effects occur, we would expect mothers and infants within the MBN condition with lower levels of risk to evidence the greatest improvement in functioning and, though not statistically significant, that MBN mothers and infants, even in the presence of high risk, would evidence higher positive change trajectories than those of DDAS mothers and infants.

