
Maintenance of Effects (Aim 4)

Maintenance affects will be viewed by single indicants for maternal and infant functioning. We estimate that our maintenance sample will be at a minimum n=150 (overall 17% attrition). For this aim, we will examine mother-infant change trajectories utilizing SEM methodology, performing Latent Growth Curve Model (LGCM) analyses, and include an Intervention indicant predicting intercept and slope estimates. This analysis will supplement our Aim 2 analyses and, if the index variables within this analysis generally reflect the acute intervention trajectories (*e.g.*, significant intervention acute effects demonstrate with constructs reflect the same differential pre-post index variable trajectory), will allow us to more strongly view the trajectory of change across time. Given the restricted nature of follow-up assessments, balancing participant burden and desire to maximize assessment completion across time, we will view these maintenance trajectories with caution.

Power Analysis

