We expect a pre-post attrition rate of 17% (n=150). For traditional PALS, across a series of randomized control studies, attrition rates ranged from 9% to 24% [26,97]; within our recent Baby-Net R01 study, we evidenced 7% attrition from pre-to- post assessment and 15% at 6-month follow-up working with low-income mothers in KS and OR, some of whom were experiencing elevated levels of depressive symptoms. In this study, a moderate to large effect size ($d=.5 - 1.03$) is anticipated for maternal outcomes and a small to moderate effect size for the infant outcome ($d=.2-.4$ for infants), based on PALS program evidence [18,27], our Baby-Net preliminary results, and evidence of CWDC [100] and Internet-based CBT treatment success [101]. We calculated the smallest effect size to be detected within a 2 x 2 analysis based on .05 alpha, a sample of n=75 per condition and viewed effects relative to a high ($r=.68$) and low ($r=.21$) repeated measures correlation. We found that with power at .95, we could detect an effect as low as $d=.37$ (with low repeated correlation) and $d=.23$ (with high correlation); with power of .80 we could detect an effect size as low as $d=.29$ (with low repeated correlation) and $d=.18$ (with high correlation). Viewing LGCM maintenance trajectories, the number of cases per estimated parameter needs to be sufficient, with a rough guideline of 5:1 [102,103]. Using this guideline, we will have sufficient sample size to estimate 34 parameters within our initial follow-up sample, with 3 time-points and a condition predictor. For our maintenance examination, as noted, we will not statistically view condition differences in trajectories, but rather will hold these examinations to a preliminary view of intervention.

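### The first-line Aim 2 test is a change-score comparison: it uses the baseline less efficiently than adjusting for it, and no method covers dyads without a post score

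*SAP*

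**What the plan says.** The SAP section on acute intervention effects (Aims 2.1–2.3) begins with a two-wave, two-group "MBN intervention group) repeated measure analysis of variance" and moves to MANOVA if the outcomes are inter-correlated. No Aim 2 analysis adjusts for the outcome's own baseline. The one analysis of covariance, in Aim 2.4, adjusts infant change for parent change.

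On who is analysed, Random Sampling/Attrition Analysis says that in general the SAP follows an intent-to-treat "approach and all participants recruited will be included in subsequent analyses". The acute-effects section then states: "Our post-assessment n, to examine acute intervention effects, is expected to be 150 (75/condition"). The protocol's Aim 2 plans to randomise 180 dyads. The only attrition procedure is a Group x Attrition Status MANOVA on baseline variables. The Aim 4 growth model is described with "This analysis will supplement our Aim 2 analyses", and no missing-data estimator is named for it.

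Power Analysis says that it "viewed effects relative to a high ($r=.68$) and low ($r=.21$) repeated measures correlation". It reports that "with power of .80 we could detect an effect size as low as $d=.29$ (with low repeated correlation") and d=.18 with high correlation. At power .95 the figures are d=.37 and d=.23.

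**The concern.** Subtracting the baseline gives it a fixed coefficient of 1, whereas regression estimates the coefficient. When the pre-post correlation is low, subtraction adds noise and can do worse than ignoring baseline altogether. The trial collects this baseline anyway, so the lost precision is avoidable.

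The second issue is the roughly 30 dyads (180 − 150) without a post score. A two-wave ANOVA drops them, so the inclusion promise has no method behind it. The attrition MANOVA can detect differential loss but cannot correct for it. Analysing only assessed dyads is not biased in itself. The change-score contrast becomes biased if loss depends on baseline differently by arm. The baseline-adjusted contrast stays unbiased in that case if scores are missing at random given baseline.

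**Working it through.** **Inputs.** From the SAP's Power Analysis: n=75 per arm (N=150), alpha .05 (taken as two-sided), r=.21 and r=.68. From the protocol's Aim 2: 180 randomised, so 30/180 = 16.7% are lost. The SAP gives no SDs. Let s = baseline SD / post SD, with post SD = 1.

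**1. Reproducing the SAP's figures.** For the group-by-time F test (df 1 and 148), the noncentrality is λ = f² × N × 2/(1−r). Power of 80% needs λ = 7.95.
- r=.21: f = √(7.95 × .79/300) = .1447, so 2f = .289 (SAP .29).
- r=.68: f = √(7.95 × .32/300) = .0921, so 2f = .184 (SAP .18).
- At 95% power, 2f = .372 and .237 (SAP .37 and .23).

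The between-group main effect does not reproduce them (2f = .36 and .42 at 80% power). The planned test is therefore the interaction, and the SAP's d is 2f. A between-arm difference in change equals 4f, that is .579 and .368 SD. These agree with the SAP on a different scale.

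**2. Identity.** On simulated two-wave data, the interaction F and the squared change-score t were both 3.5704.

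**3. Variances of the arm contrast.**
- Change score: (1 + s² − 2rs) × 2/n
- Baseline-adjusted: (1 − r²) × 2/n
- Post score only: 2/n

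The first minus the second is proportional to (s − r)², so it is never negative. The first exceeds the third when r < s/2. At s=1 the adjusted/change ratio is (1+r)/2. At r=.21, 75 × .605 ≈ 45 per arm with adjustment matches 75 per arm on change scores; at r=.68 it is 75 × .84 = 63.

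**4. Difference detectable with 80% power, 75 per arm (post-SD units).**

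| s | r | Variance ratio | Change score | Adjusted |
|---|---|---|---|---|
| 1 | .21 | .605 | .58 | .45 |
| 1 | .50 | .75 | .46 | .40 |
| 1 | .68 | .84 | .37 | .34 |
| .8 (assumed) | .21 | .733 | .53 | .45 |
| .8 (assumed) | .68 | .974 | .342 | .338 |

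Post scores alone give .46, so at r=.21 the planned test does worse than ignoring baseline.

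**5. Power at s=1, change score v adjusted.**

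| Difference | r=.21 | r=.68 |
|---|---|---|
| .2 | 16% v 24% | 33% v 38% |
| .4 | 49% v 70% | 86% v 91% |
| .5 | 68% v 88% | 97% v 99% |
| .8 | 97% v over 99% | about 100% for both |

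The SAP anticipates d=.2–.4 for infants without stating the scale. On its 2f scale, the rows that apply are .4 to .8.

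**6. Bias from loss (assumed mechanism).** Take loss of 1/6 per arm, depending on baseline in one arm only, with a log-odds slope of .5 to 1 per baseline SD. Among dyads kept, the baseline gap between arms is then about −.08 to −.145 SD. The change-score bias is (r − 1) × gap.
- r=.21: .79 × .08 = .063 to .79 × .145 = .115 (simulated .063 and .113).
- r=.68: .32 × .08 = .026 to .32 × .145 = .046 (simulated .026 and .047).

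With 90 randomised per arm (6,000 trials), type I error is 6.0–8.6% at r=.21 and 5.4–6.5% at r=.68. Adjusted bias is about 0 (type I error 4.6–5.7%). If loss depends on baseline equally in both arms, change-score bias is also about 0.

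**7. What imputation adds.** With loss at random and r=.21, empirical SDs over 1,000 trials are .220 (change), .169 (adjusted, complete cases) and .171 (imputed from baseline alone), so there is no gain in precision. Now suppose a second baseline variable, with coefficient .4 on the post score, drives loss in one arm at slope 1. Complete-case adjusted bias is then −.056 (r=.21) and −.052 (r=.68), against .004 and .007 after imputation using that variable.

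**The case against.** The planned test is valid under randomisation, and Aims 2.1–2.3 are worded as change, which it answers directly. The gain cannot be fixed from the documents, because it depends on each outcome's r, the SD ratio and the scale of the anticipated d. Mothers enter above a depression cut-off, so a baseline SD below the post SD is plausible for depression, and at a given r that shrinks the gain. If the maternal d=.5–1.03 is on the 2f scale, the between-arm difference is at least 1.0 SD and power exceeds 99% either way. The loss mechanisms are assumed. At the mild end (slope .5, r=.68) a 20,000-trial run gave type I error of 5.1%, close to nominal. The nearest statement in the SAP, "we will examine if higher levels of depression are associated with low dosage only within the Mom and Baby Net (MBN) intervention group", concerns dosage rather than assessment loss, and the SAP does not expect that pattern.

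These points limit the size, and they stand.

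Two others carry less weight. Aim 4 does include an intervention predictor of intercept and slope. But that model is supplementary, no missing-data estimator is named, and Power Analysis says "we will not statistically view condition differences in trajectories". Separate regressions for about six outcomes carry no multiplicity rule, but neither do the SAP's own univariate ANOVAs, and the joint MANOVA can be kept as a sensitivity analysis.

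**Conclusion.** The concern holds, mainly as an avoidable loss of precision. The change-score test is valid but, apart from one degree of freedom, never more precise than baseline adjustment. The loss is large at the SAP's low correlation, modest at its high one with equal SDs, and close to nil at r=.68 if the baseline SD is .8 of the post SD. The variance formulas assume a baseline unaffected by assignment.

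Separately, the promise to include everyone has no method behind it for the roughly 17% without a post score. Bias of about .06–.11 SD (r=.21) or .03–.05 SD (r=.68) would follow only under the assumed one-arm dependence of loss on baseline, which nothing in the documents reports. The change should be made, but the planned analysis is not invalid without it.

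**What to change.** **Estimate.** For each Aim 2 outcome, use the arm coefficient from a regression of post score on arm and baseline score, with all randomised dyads analysed as assigned.

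**Missing post scores.** The regression alone still drops these dyads. Impute by arm under a stated missing-at-random assumption, using baseline and other collected predictors of loss, such as contextual risk, depression chronicity and other treatment. Report how many randomised dyads have no assessment at all; they add no information under any of these models.

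**Alternative.** A joint pre/post likelihood model with a common baseline mean would serve, for dyads assessed before randomisation only. Do not use its unconstrained form as the check: on complete data it returns the change-score contrast (.5090 for both in a simulated example, against .3772 adjusted).

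**Remote dyads.** The protocol's COVID Remote Procedures place randomisation before a pre-assessment run by the assigned coach. Repeat the adjusted analysis without these dyads.

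**Sensitivity analysis.** Keep the repeated-measures ANOVA/MANOVA. This retains the joint test and the change scores that Aims 2.4 and 3 reuse.

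**Cost.** SAP wording, modest programming for imputation, and an in-home/remote flag for each pre-assessment. No new measurements. The Aim 2 estimate would no longer come from the change scores used in Aims 2.4, 3.2 and 3.3, and the SAP should say so.

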METHODOLOGICAL PROCEDURES & DOCUMENTS MANUAL

Reducing Maternal Depression and Promoting Infant
Social-Emotional Health & Development

NIH R01 HD086894

NCT03464630

Randomized Controlled Trial Design: Prior to iPhone set up, the Intervention Project Coordinator implements randomization procedures. Using a random number generator, mother-infant dyads were randomized, in a 1:1 allocation, to one of the two parallel interventions: Mom and Baby Net or Depression and Developmental Awareness. The Intervention Project Coordinator notifies the PI to review condition assignment and assigns case to intervention coach. (see pages 26 and 98 in Procedures below)

Objective and Specific Aims:

The objective of this project was to address the problem of silo interventions and to improve accessibility to intervention that both reduces maternal depression and improves infant social emotional and communication development. To achieve this objective the following specific aims were addressed:

1. Embed core components of the Mom-Net Internet intervention into the Internet based virtual coaching intervention, Baby Net, to create Mom and Baby Net, an instructionally sound program geared to reduce the internal demands of depressed mothers postpartum.
2. Evaluate the impact of the Mom and Baby Net (MBN) program, as compared to a parallel Internet remote coaching intervention: Depression and Developmental Awareness (DDAS), via a randomized controlled trial. Depressed mothers during the postpartum period and their infants (N=180 dyads) will be randomized to the MBN or DDAS . Impact will be examined relative to:
 - 2.1 Change in parenting behavior, attitudes, beliefs, knowledge, and stress;
 - 2.2 Infant social-emotional behavior and development change;
 - 2.3 maternal depressive symptoms change; and
 - 2.4 Concomitant change in parenting, infant social-emotional, and maternal depressive symptom outcomes as a result of intervention.
3. Evaluate moderating influences on parent and infant behavior within the context of depression during the post partum period. We will focus on:
 - 3.1 The extent to which maternal depression prior to intervention, including current depression symptoms as well as depressive history and chronicity, relate to dosage within the MBN program;
 - 3.2 How dosage moderates parent and infant behavioral change as well as maternal depressive symptom change; and

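### Aim 2.4 expects a strong parent–infant link to make the intervention effect non-significant, which is not true in general; the effect explained and its proportion are planned without an interval (minor)

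*SAP*

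**What the plan says.** Protocol Specific Aim 2.4 is to examine "Concomitant change in parenting, infant social-emotional, and maternal depressive symptom outcomes as a result of intervention". In the SAP, under Examination of Acute Intervention Effects, each mother's and infant's pre–post change becomes a trajectory score, and infant change is analysed by ANCOVA with parent change as covariate. The SAP offers this as one approach and describes no other. The steps are:

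- A test of the link: "We will determine whether the parent change covariate is significantly related to the dependent variable".
- The intervention effect size and its significance with the covariate ignored.
- The comparison: "We will then determine if entering the parent functioning covariate modifies the intervention effect size and statistical significance".
- The expectation: "If parent change is strongly linked to infant change, then entering the covariate should result in nonsignificant intervention effects".
- The share explained: "Estimates of covariance-adjusted effect sizes will provide estimates of the proportion of intervention effect size that can be explained by the parenting change variable".
- A test of whether the parent–infant association differs by arm.

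The intervention effect on parent outcomes is tested separately, under Aims 2.1–2.3. The SAP states no interval for the reduction in effect or for the proportion explained.

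**The concern.** The expectation conditions on the parent–infant link alone. How far the intervention effect shrinks depends on the link and on how much the intervention moves parent change. Whether it then crosses the significance threshold depends also on any remaining direct effect and on precision. A significant covariate beside a still-significant adjusted effect is ordinary partial mediation, yet the sentence says it should not occur. An analyst who takes the sentence at its word could read that result as evidence against mediation.

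The proportion explained divides by the infant effect, which the SAP expects to be small to moderate. Reported as a bare point estimate, it could be taken as more precise than it is. What is at stake is the interpretation of Aim 2.4 only.

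**Working it through.** **Inputs from the SAP.** 75 per condition after attrition; alpha .05 (taken as two-sided); maternal d .5 to 1.03; infant d .2 to .4; repeated-measures correlation r = .21 or .68.

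**Assumed, because the documents do not give them.** The within-arm parent–infant correlation (the link), the share mediated, and the scale of d.

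**Step 1: the SAP's own power figures.** For the group-by-time interaction take the noncentral F(1,148) with λ = f²·150·2/(1−r) and f = d/2. At r = .21, power is .95 at d = .37 and .80 at d = .29. At r = .68 it is .94 at d = .23 and .78 at d = .18. This matches the stated .95 and .80 within 2 points, so the Power Analysis appears to use d = 2f. In change-score SD units that d equals 2d/√(2(1−r)), a multiplier of 1.59 (r = .21) or 2.5 (r = .68). Since the anticipated d may not have been meant on this scale, results are given both ways, with the multiplier applied to maternal and infant d alike.

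**Step 2: what adjustment does.** With both change scores scaled to within-arm SD 1, b is the link and the total infant effect is c = c' + a·b. Then

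- total: z = c / √(2/75)
- adjusted: z = (c − a·b) / √[(1 − b²)(2/75 + a²/150)]

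Outside the SAP's ranges:

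- a = 0, link .6, c = .4: z rises from .4/.163 = 2.45 to .4/(.8 × .163) = 3.06. The adjusted effect is significant in 86%.
- a = .5, link .6, direct effect .4 (so c = .4 + .5 × .6 = .7): adjusted z = .4/(.8 × .168) = 2.97. Significant in 84%.

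Inside the SAP's ranges, percentage of trials with the adjusted effect still significant:

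| Maternal d, infant d | Scale | Link .4 | Link .5 | Link .6 |
|---|---|---|---|---|
| .5, .4 | change-SD | 25 | 17 | 12 |
| .5, .4 | d = 2f, r = .21 | 49 | 34 | 20 |
| .5, .4 | d = 2f, r = .68 | 80 | 61 | 36 |
| .5, .3 | d = 2f, r = .68 | 29 | 12 | 5 |
| .75, .4 | d = 2f, r = .68 | 23 | 7 | 11 |

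The formula shows where these come from. In the third row at link .4, a = 1.25 and c = 1.0, so c' = .5 and z = .5/√(.84 × .0371) = 2.83, or about 80%. In the last row at link .6, a·b = 1.875 × .6 = 1.125 exceeds c = 1.0. The adjusted effect is then negative, and nearly all of that 11% is reversed in sign.

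**Step 3: loss of significance as a sign of mediation.** Count trials in which the total effect is significant and the adjusted effect is not. Under half mediation (c' = a·b) with maternal d = .75 and r = .68 on the d = 2f scale, this happens in 66/60/37% at infant d = .2/.3/.4. It becomes less frequent as the infant effect grows, although half the effect is mediated throughout.

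**Step 4: the proportion explained, a·b/c.** True value .5, maternal d = .75; central 95% of simulated estimates:

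| Infant d | change-SD | d = 2f, r = .68 |
|---|---|---|
| .2 | about −4 to 5 | −0.1 to 1.7 |
| .3 | about −1 to 3.5 | 0.10 to 1.1 |
| .4 | 0.14 to 2.0 | 0.20 to 0.91 |

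Percentages and ranges are from simulation with at least 20,000 trials per cell. The outer limits in change-SD units move by a few tenths between runs.

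**The case against.** Much of the case for leaving the text alone stands.

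- *A reader might infer that the plan never combines the two paths.* It does. In this linear model the unadjusted minus the adjusted effect equals a·b exactly, so the planned effect sizes and proportion give the combined quantity as a point estimate. The paths a and b are also each tested. Only the interval is missing.
- *A reader might infer that partial mediation could not be read from the output.* It could. It would show as a partial drop in effect size and a partial proportion explained. The fault is that the quoted expectation points the other way.
- *A reader might infer that loss of significance is a decision rule.* The SAP states it as an expectation under one approach, and no later analysis depends on it. The covariate test also limits false claims. With no link at all, significance is lost in 4–14% of trials (change-SD) or 0–42% (d = 2f), but in only 0.4–1.2% or 0.0–2.2% once a significant covariate is also required.
- *A reader might infer that the expectation usually fails.* The largest in-range figures come from one corner: lowest maternal d, highest infant d, and the scale that multiplies d by 2.5. Away from that corner it often holds.
- The proportion explained is not unstable everywhere. At infant d = .4 with r = .68 on the d = 2f scale its spread is moderate.
- The protocol words Aim 2.4 as concomitant change, which the covariate and heterogeneity tests address directly.

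What remains is a false general statement about what a strong link implies, and two estimates planned without an interval.

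**Conclusion.** The point holds in this limited form and is minor. The sentence is wrong as a rule because attenuation depends on a·b and not on b alone. At the SAP's lowest maternal and highest infant effect, a strong link leaves the adjusted effect significant in 12–25% of trials in change-SD units and in 20–80% on the scale that reproduces the SAP's power figures. When a is large relative to the infant effect, the expectation mostly comes true. The proportion explained needs an interval, chiefly at infant d of .2 to .3 or on the less favourable scale. These sizes rest on assumed links of .4 to .6, on the assumed share mediated, and on the scale of d, none of which the documents settle. The algebra does not depend on them. Aims 2.1–2.3 are unaffected.

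**What to change.** Replace the sentence with wording such as: *Entering parent change is expected to reduce the intervention effect by a·b; a change in statistical significance will not be used as evidence of mediation.* Keep every planned analysis. In addition:

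- Report the planned reduction in effect (c − c', equal to a·b) with a percentile bootstrap 95% confidence interval, resampling dyads within arm.
- Report the proportion explained only with its interval from the same bootstrap.
- If the planned heterogeneity test shows that slopes differ by arm, report by arm.
- State that parent and infant change cover the same pre–post interval, so the result is associational.

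The cost is a few lines of SAP text and analysis; no new data are needed. The downside is wide intervals. In change-SD units the median width is .25–.40 SD for a·b. For the proportion (truth .5, maternal d = .75) it is 7.9/3.9/1.9 at infant d = .2/.3/.4. Bootstrap coverage in that setting was 94–96% for a·b and 95–99% for the proportion; it was not checked on the d = 2f scale.

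### Aim 2.4 makes no allowance for measurement error in the two-wave parent change score, so the planned 'proportion explained' may be well off, and a residual intervention effect after adjustment is not evidence against a parenting pathway

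*SAP*

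**What the plan says.** The SAP (Examination of Acute Intervention Effects, Aim 2.4) uses polynomial contrasts to "produce individual trajectory scores reflecting parent and infant change from pre to post". Infant change is then the dependent variable of an ANCOVA with parent change as the covariate. The outputs are a test that the two changes covary, the intervention effect with and without the covariate, and a test of whether the association differs by group. On the second of these the SAP says: "Estimates of covariance-adjusted effect sizes will provide estimates of the proportion of intervention effect size that can be explained by the parenting change variable". It adds that, if the link is strong, the adjusted intervention effect should lose significance. The method is introduced as one approach, but no other is described.

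The Constructs paragraph uses SEM to confirm each construct. The score then analysed is an observed unit-weighted sum, or one index variable if the fit is poor. Depression, knowledge and stress are single indicants. Adequate internal consistency and inter-rater reliability are required, but no value is given. The Aim 4 growth model concerns maintenance and does not re-estimate this proportion.

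The only pre-post correlations are in the Power Analysis, which "viewed effects relative to a high ($r=.68$) and low ($r=.21$) repeated measures correlation". They are not assigned to any particular outcome.

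**The concern.** With two waves, the linear contrast is post minus pre up to a constant. A difference score is usually less reliable than the scores it is built from, and the loss grows as the pre-post correlation rises. The ANCOVA nevertheless treats it as measured without error. Random error in a covariate flattens its slope, so the covariate removes less of the intervention effect than true parent change would. A larger sample does not cure this.

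The stake is the reading of Aim 2.4. Parenting could carry much of the infant effect and the analysis would still leave a residual intervention effect and report a modest proportion. Error shared between mother and infant scores could instead inflate the proportion.

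**Working it through.** **1. Inputs.** From the SAP: two waves; r = .21 and .68; 75 per condition; anticipated effects d = .5-1.03 (maternal) and .2-.4 (infant). Assumed here: reliability R of one parent assessment. The main range is .75-.90 and the wider range .70-.95.

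**2. The plan's own figure.** The SAP's detectable effects are "based on .05 alpha, a sample of n=75 per condition". Take the group-by-time interaction F test with N = 150, m = 2 waves, df 1 and 148, noncentrality N·m·f²/(1 − r), and d = 2f. This gives d = .372 (r = .21) and .237 (r = .68) at power .95, and .289 and .184 at power .80. The SAP prints .37, .23, .29 and .18. The figures reproduce, so r is the ordinary pre-post correlation. The SAP states no reliability and no expected proportion explained.

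**3. Attenuation.** With equal variances at the two waves and independent errors, the reliability of the difference score is λ = (R − r)/(1 − r). Let a be the group difference in mean parent change, c the total effect on infant change, and b the within-group slope. The proportion reported is b·a/c. Random error leaves a and c unchanged on average and multiplies b by λ. So reported proportion = λ × true proportion, and the understatement is 1 − λ.

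Example: R = .80, r = .68 gives λ = .12/.32 = .375, an understatement of 62.5%.

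| R (assumed) | λ, r = .21 | understated | λ, r = .68 | understated |
|---|---|---|---|---|
| .70 | .620 | 38% | .062 | 94% |
| .75 | .684 | 32% | .219 | 78% |
| .80 | .747 | 25% | .375 | 62% |
| .85 | .810 | 19% | .531 | 47% |
| .90 | .873 | 13% | .688 | 31% |
| .95 | .937 | 6% | .844 | 16% |

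Simulation of full mediation (75 per arm, parent effect .5 SD) agrees. For R = .75, .80, .90 the reported proportion is .69, .74, .87 at r = .21 and .22, .38, .69 at r = .68; the truth is 1.

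**4. When the assumptions fail.** Take a = .5, c = .3, unit variance at each wave and the same r for the infant. Let w be the correlation of parent change error with the infant residual. For true proportion P, set β = P·c/a and s² = 2(1 − r) − β²·2(R − r). Then

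reported = λP + w·(a/c)·s·√(2(1 − R)) / (2(1 − r)).

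- P = .5, w = .3, R = .75, r = .68: β = .3, s² = .64 − .09 × .14 = .627, s = .792. Reported = .109 + .3 × 1.667 × .792 × .707/.64 = .109 + .438 = .55. The other three corners (R = .75 or .90, r = .21 or .68) give .61. Understatement has become slight overstatement.
- P = 0, w = .2: the formula reduces to .2 × 1.667 × √((1 − R)/(1 − r)). This is .12 at R = .90, r = .21 and .29 at R = .75, r = .68, with no true mediation.
- Common cause loading .4 on both changes, P = .5, R = .90, r = .21: s² = 1.58 − .09 × 1.38 = 1.456, s = 1.207. Reported = .437 + .16 × 1.667 × √1.38 × 1.207/1.58 = .437 + .239 = .68.
- Parent errors correlated φ = .4 across waves: λ = 1 − (1 − R)(1 − φ)/(1 − r). At R = .75, r = .68 this is 1 − .25 × .6/.32 = .53 instead of .22.

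**5. What correction costs in precision.** Simulated full mediation, 75 per arm, infant effect .3, known error variance, R = .75, r = .68: the corrected ratio centres near 1.0, but its central 95% range is roughly −3 to 10, and about 32% of estimates fall below 0 or above 2.

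**The case against.** A reader might infer that the SAP's own correlations imply an understatement of 13-78%. They do not. Half of that calculation is a reliability that neither document gives, and .21 and .68 are generic power inputs. A reader might also infer that the bias is always downward. The documents do not support that: the mother answers for herself and her infant, and both appear in the same videos, so shared error is plausible.

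Further points stand:

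- The 78% figure is a corner case. R = .75 with r = .68 implies a true-score pre-post correlation of .68/.75 = .91, so mothers would hardly differ in true change. At r = .21 the loss is 13-32%.
- The protocol words Aim 2.4 as concomitant change resulting from intervention, and the proportion is one of several outputs. The pathway reading comes from the SAP's proportion-explained language and its loss-of-significance rule.
- Replacing the ANCOVA with a latent change model is tempting but not justified. The corrected ratio can be too unstable to use at this sample size. If parent and infant outcomes are each one score, a free same-occasion error covariance is not identified.
- Correcting for reliability does not deal with confounding. In the common-cause example, .68/.873 = .77, further from the true .50.

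None of this supplies the missing allowance for error. It limits what can be said about size and direction, and argues for a sensitivity analysis beside the planned one.

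**Conclusion.** The gap is real and the claim is conditional. With R = .75-.90, independent errors, equal variances, no common cause of the two changes and r between .21 and .68, the understatement is about 13-32% at the low correlation and 31-78% at the high one. Over R = .70-.95 the full span is 6-94%. It vanishes only with error-free measurement. Shared-source error or confounding can offset or reverse it, so neither size nor sign is known in advance.

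It follows that a residual effect after adjustment does not count against a parenting pathway, and a large proportion does not establish one. The group comparisons under Aims 2.1-2.3 do not use this covariate and are not affected. This is an inexpensive improvement to a secondary analysis.

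**What to change.** In the Aim 2.4 text:

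- Keep the planned ANCOVA. Add a reliability-corrected sensitivity analysis (errors-in-variables or latent change), using the trial's own baseline reliability estimates and a stated range around them.
- Report the indirect effect, the product of the two paths, with a bootstrap interval. Do not rely on the ratio alone.
- Allow correlated same-occasion parent and infant errors only where multiple indicants identify them. Otherwise vary that correlation over a stated range.
- Remove the rule that loss of significance shows mediation.
- State that the proportion is associational, because parent change is not randomised, and that a residual effect is not evidence against a parenting pathway.

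Cost: SAP wording and a little more analysis for each parent outcome. The corrected results depend on a stated reliability, and their intervals will be very wide when reliability is close to the pre-post correlation.
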